APPENDIX 3. RESCUE MEDICATIONS

Rescue medications should only be considered after non-medical interventions have been exhausted. Under all circumstances, only the study site-designated physician will administer rescue medications in this study. The choice of rescue medications is at the discretion of the study site-designated physician and should be based on subject medical history and local standard of care.

The unique pharmacologic properties of individual rescue medications (e.g., rapidity of onset, persistence of active drug or metabolite in the body) should be considered for rescue and considered along with a subject's sex, age, weight and/or comorbidities.

The study site-designated physician must consider rescue medications and if they have been associated with lengthening QTc interval, which can lead to syncope, arrhythmia or sudden cardiac arrest.

Other Considerations:

- Adjustment of doses for non-smokers versus moderate to heavy smokers.
- Concurrent use of IM and IV benzodiazepines and neuroleptics, individually or concomitantly, is not recommended outside of an emergency setting because of the need to monitor (e.g., a respiratory depression).
- If a rescue medication is considered, monitoring parameters include mental status/alertness, vital signs, neuropsychiatric signs and symptoms, delirium, fever, muscle rigidity, and/or autonomic instability, and risk of falling. Follow-up with ECG as needed.

Examples of acceptable rescue medications including benzodiazepines, neuroleptics, and antiemetics are shown in Table 10, Table 11, and Table 12. These tables are not meant to be exhaustive.

Table 10: Examples of Rescue Benzodiazepines: Dosing

Drug	Adult oral doses (mg)
Alprazolam	0.5 to 6
Clonazepam	0.5 to 4
Diazepam	4 to 40
Larazanam immadiata ralaga	0.5 to 6
Lorazepam immediate release	0.5 to 4 (hypnotic)

Clinical Study Protocol: MMED008

Table 11: Examples of Rescue Neuroleptics: Dosing

Agent	Initial oral dose range (mg)	Adjustment of oral dose in older subjects
Olanzapine	5 to 10	1.25 to 2.5 mg
Quetiapine	50 (immediate release) 300 (extended release)	25 to 50 mg
Risperidone	1 to 2	0.25 to 0.5 mg

Table 12: Examples of Medications for Nausea

Nausea is a known and tolerable effect of this compound. Supportive solutions are the best first line treatment, please refer to DSMM.

Drug	Dosing
Benzodiazepines	Refer to Table 10 for appropriate doses
Ondansetron	8 mg q12 hr
Promethazine	25 mg q12 hr

Signature Page for VV-CLIN-000052 v1.0

## **1** INTRODUCTION

This statistical analysis plan (SAP) describes the planned statistical analysis to be performed for the study, MMED008 entitled "A Phase 2, Multi-center, Randomized, Double-Blind, Parallel-Group, Dose-Finding Study to Assess the Effect of Four Doses of MM-120 for the Treatment of Anxiety Symptoms." Analysis and the statistical analysis described in this SAP, including production of all tables, figures and listings. This SAP denotes the final analysis of the study, and does not include any formal interim analysis.

## **2 OBJECTIVES AND ENDPOINTS**

## 2.1 Objectives

## 2.1.1 Primary Objective

The primary objective of the study is to determine the dose-response signal and assess the dose-response relationship of 4 doses of MM-120 (25, 50, 100 or 200  $\mu$ g freebase-equivalent) as measured by the change in Hamilton Anxiety Rating Scale (HAM-A) Total Score from Baseline to Week 4.

## 2.1.2 Secondary Objectives

The key secondary objective of the study is to determine the dose-response signal and asses the dose-response relationship of the 4 doses of MM-120 (25, 50, 100 or 200  $\mu$ g freebase-equivalent) as measured by the change in HAM-A Total Score from Baseline to Week 8. Other secondary objectives are:

- To determine the dose-response signal and assess the dose-response relationship of the 4 doses of MM-120 (25, 50, 100 or 200 µg freebase-equivalent) as measured by the change in HAM-A Total Score from Baseline to End of Study,
- To determine whether MM-120 (25, 50, 100 or 200 µg freebase-equivalent) improves functionality and quality of life measures in subjects with anxiety symptoms, including improvements in the following:
  - Depressive symptoms
  - Anxiety symptoms
  - Functional disability
  - Quality of life
  - o Sleep
  - Sexual function

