4.3. End of Study Definition

End of Study is defined as the date when the last subject has either completed the last study visit, has discontinued from the study, or is lost to follow-up (i.e., the site/Investigator is unable to contact the subject).

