10.2.2.4. Secondary Efficacy Endpoints

Change from Baseline to Week 1, Week 2 (as applicable), Week 4, Week 8 and End of Study (as applicable) in HAM-A, MADRS, CGI-S, CGI-I, PGI-S, PGI-C, SDS, EQ-5D-5L, PSQI and ASEX will be analyzed descriptively. Continuous outcomes will be summarized by: n, mean, standard deviation, median, Q1 (25th percentile), Q3 (75th percentile), minimum, maximum and 95% Confidence Interval for the mean. For the active doses similar statistics will be reported for the difference from placebo. Categorical measures will be summarized by the number and percentage of subjects within each category.

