## 4.5 Handling of Dropouts or Missing Data

Missing data on demographics, baseline information and safety measures will be treated as missing; no imputation is planned.

Missing or partial dates and times will be imputed for analysis purposes in a manner that imputes the most conservative date or time. Imputation methods for dates and times are described for each endpoint where applicable.

Details of missing data imputation will be specified in the analysis methods for the primary and key secondary efficacy endpoints. Subject-completed questionnaires will be considered missing if incomplete. Missing data will not be imputed for analysis of non-key secondary efficacy endpoints or safety endpoints.

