## 4.6 Multiple Comparisons

The Multiple Comparison Procedure – Modeling (MCP-Mod) method will be used to assess the primary endpoint. Details of the method is provided in Section 6.1 below.

A hierarchical (i.e., simple fixed sequence testing) testing strategy will be used to protect the overall type I error rate when testing the primary efficacy endpoint with the key secondary efficacy endpoint.

No adjustment for multiplicity will be performed for testing the non-key secondary and exploratory endpoints.

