## 6.2 Key Secondary Efficacy Endpoint and Analysis

## 6.2.1 Key Secondary Endpoint

The key secondary endpoint is change from Baseline to Week 8 in HAM-A Total Score. Analysis of this endpoint will follow the same process as the primary endpoint described in Section 6.1. The outcome for this endpoint will be considered confirmatory, if in agreement with the primary endpoint outcome and provided that the null hypothesis is rejected for the primary outcome. This gatekeeping function of the primary outcome allows for no adjustment of alpha level for multiplicity of testing.

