## 6.3.1 Change from Baseline in HAM-A Total Score

In addition to the primary and key secondary analysis for HAM-A, descriptive statistics will be presented for actual values and change from Baseline for scheduled visits. The change from Baseline will be analyzed using an analysis of covariance (ANCOVA) model including change from Baseline HAM-A Total Score as dependent variable, the baseline HAM-A Total Score as a covariate and treatment group as a fixed effect. The Least Square Means (LS Means) for each treatment group compared to placebo will be reported along with associated 95% CI and p-value. The ANCOVA comparisons will be performed for Week 1, Week 2, Week 4, Week 8 and the End of Study visit and will be presented for both the FAS and PPS populations.

A by-subject listing of results by visit, including any unscheduled visits, will be provided.

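### The secondary objective on HAM-A dose-response at End of Study is not answered by the planned analysis, which compares each dose with placebo but specifies no dose-response test or fitted curve

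*SAP*

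**What the plan says.** Among the other secondary objectives, SAP 2.1.2 lists "To determine the dose-response signal and assess the dose-response relationship of the 4 doses of MM-120", "as measured by the change in HAM-A Total Score from Baseline to End of Study". The Protocol Synopsis and Protocol 3 carry the same objective. The primary (Week 4) and key secondary (Week 8) objectives have the same form.

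The analyses assigned to the three visits differ:

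- **Week 4** (SAP 6.1.1 and 6.1.2): multiple imputation, a six-contrast MCP test against a common critical value, then model averaging and target-dose estimation.
- **Week 8** (SAP 6.2.1): "Analysis of this endpoint will follow the same process as the primary endpoint described in Section 6.1".
- **End of Study** (SAP 6.3.1): descriptive statistics and an ANCOVA of each treatment group against placebo, with 95% CI and p-value, on the FAS and PPS. "The ANCOVA comparisons will be performed for Week 1, Week 2, Week 4, Week 8 and the End of Study visit".

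Two general rules apply to End of Study as a non-key secondary endpoint. SAP 4.5: "Missing data will not be imputed for analysis of non-key secondary efficacy endpoints or safety endpoints". SAP 4.6: "No adjustment for multiplicity will be performed for testing the non-key secondary and exploratory endpoints". Protocol 10.2.2.4 places End of Study HAM-A change in a list of scales whose sentence ends "PSQI and ASEX will be analyzed descriptively". The SAP addendum adds HAM-A subscale ANCOVAs and adverse event tables, and states that it changes none of the planned analyses.

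**The concern.** The plan gives its dose-response wording a definite meaning. At Weeks 4 and 8 the signal is a maximum contrast test that either crosses a critical value or does not, and the relationship is a model-averaged curve. For End of Study neither is specified. There is no contrast or trend test, no fitted model, and no rule for turning four comparisons with placebo into a statement about a signal.

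Whoever reports on this objective will therefore have to read a pattern from four unadjusted, observed-case p-values. Two readers could reach different answers from the same table. The protocol and the SAP also differ on whether p-values belong there at all. What is at stake is whether a stated secondary objective can be answered as written.

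**Working it through.** **Inputs** (SAP 9, 6.1.2 and 3.2.1). Doses 0, 25, 50, 100, 200 µg; 36 per arm; 1:1:1:1:1 allocation; common SD, set to 1; maximum standardized effect 0.6; one-sided 5%; six candidate shapes. Residual df = 180 − 5 = 175. The baseline covariate is given no credit, and no dropout is applied.

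**MCP-Mod.** For shape k with means μ_k scaled to a maximum of 0.6, the optimal contrast with equal arms is c_k ∝ μ_k − mean(μ_k), scaled to length 1. The statistic is T_k = √36 · c_k′ȳ / s. The critical value is the 95th percentile of max(T_1,…,T_6) under a flat curve, about 2.045. Power is P(max T_k ≥ 2.045) under each shape (Monte Carlo, 1,000,000 draws).

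**Reading four comparisons.** T_d = (ȳ_d − ȳ_0) / (s√(2/36)). Any favourable unadjusted result means max T_d exceeds the two-sided 5% t critical value.

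| Shape | Stated MCP-Mod power (%) | Reproduced (%) | Any favourable unadjusted p-value (%) |
|---|---|---|---|
| Sigmoid 10, 1 | 84.5 | 84.5 | 89.3 |
| Sigmoid 100, 5 | 90.7 | 90.7 | 73.9 |
| Sigmoid 100, 10 | 91.0 | 90.9 | 73.8 |
| Sigmoid 150, 10 | 89.9 | 89.8 | 71.8 |
| Emax 100 | 83.2 | 83.2 | 79.5 |
| Linear | 85.0 | 85.0 | 74.1 |
| Mean | 87.38 | 87.35 | 77.1 |

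The SAP's own table is reproduced to within 0.1 point, so the inputs are the ones the sponsor used.

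**Error rates are not equal in that table.** Under a flat curve, four two-sided 5% comparisons sharing one placebo arm give at least one favourable result 7.8% of the time, and at least one in either direction 15.5% of the time. MCP-Mod is held at 5%.

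**Matched comparison.** With the cut-off for max T_d raised so that the favourable-direction error is also 5%, mean power is 70.3%. For sigmoid (10, 1) it is 84.3%, level with MCP-Mod. The other five shapes average (6 × 70.3 − 84.3)/5 = 67.5%, against (90.7 + 90.9 + 89.8 + 83.2 + 85.0)/5 = 87.9% for MCP-Mod.

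**Why they differ.** Take the linear shape: means 0, 0.075, 0.15, 0.3, 0.6, average 0.225. The sum of squared deviations is 0.0506 + 0.0225 + 0.0056 + 0.0056 + 0.1406 = 0.225, so the contrast noncentrality is 6 × √0.225 = 2.85. The 200 µg comparison with placebo has 0.6 × √(36/2) = 2.55 and the 100 µg comparison 0.3 × √18 = 1.27. The contrast uses all five arms; each comparison uses two. At two-sided 5% on the normal approximation those two comparisons have Φ(2.55 − 1.96) = 72% and Φ(1.27 − 1.96) = 25% power.

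**The case against.** The strongest reply is that the tiering looks intended. Protocol 10 assigns MCP-Mod to the primary outcome measure, Protocol 10.2.2.3 extends it to the key secondary endpoint, and everything below is descriptive, unimputed and unadjusted. No passage promises MCP-Mod at End of Study. By-dose LS means with confidence intervals are a legitimate display of response against dose, and Week 8 is the designated durability endpoint (Protocol 2.2.2). On this view only the objective's wording is loose. Much of this stands, and it is why rewording is an acceptable remedy. It does not remove the mismatch, because the objective still asks for something the analysis does not deliver.

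Three stronger readings are tempting, and the documents do not support them:

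- *That the endpoint is left unanalysed.* SAP 6.3.1 gives estimates, intervals and p-values by dose on two populations.
- *That the plan declares a signal on any p-value below 5%.* It states no such rule. The 7.8% and 15.5% figures show what would follow if a reader adopted one, and are not operating characteristics of the plan.
- *That the visit is undefined.* Protocol 4.3 does say "End of Study is defined as the date when the last subject has either completed the last study visit", but that is the end of the trial as a whole. The Schedule of Activities labels Visit 9 as both Week 12 and End of Study, SAP 7.2 places the End of Study visit at Week 12, and SAP 4.3 assigns HAM-A data to windows by study day, including early-withdrawal assessments. At most a cross-reference is missing.

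The power comparison also favours MCP-Mod by construction, since the true curves are its own candidate shapes.

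**Conclusion.** The mismatch is real and limited. The End of Study dose-response objective has by-dose estimates but no test of a signal and no fitted relationship, although the plan already contains a method for both. Week 4 and Week 8 inference, error control and power are untouched, and End of Study lies outside the testing hierarchy.

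Under the planning assumptions, the method already in the plan has mean power of about 87% at one-sided 5%. The best of four comparisons has about 70% at the same error rate, or about 77% if 7.8% favourable-direction error is accepted. These figures assume that the 0.6 SD maximum effect holds at Week 12, that all 36 per arm are evaluable, and that the true curve is one of the six candidates. The documents state none of these for Week 12. The advantage is about 20 points on average over five shapes and negligible for the early-plateau shape (ED50 10, hill 1). The mismatch itself does not depend on the power figures. It is worth considering, not essential.

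**What to change.** In SAP 6.3.1, add wording such as: *The imputation and MCP-Mod process of Sections 6.1.1 and 6.1.2 will also be run for change from Baseline to Week 12 on the FAS, as a supportive analysis outside the testing hierarchy. End of Study here means the Week 12 window of Table 1.* Amend SAP 4.5 to permit imputation for this one analysis.

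The cost is small but not nil:

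- The existing programs are reused for one more visit, with no new data.
- The blinded impact assessment of concomitant and prohibited medications has to extend to Week 12.
- There is one more p-value to label as supportive.
- If the analysis is added after unblinded review of the primary endpoint, it must be labelled ad hoc, as the SAP addendum (Section 1) does for its own additions, and it carries less weight.

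If the sponsor intends End of Study to be descriptive, the alternative is to reword the objective in the Protocol Synopsis, Protocol 3 and SAP 2.1.2 to match the by-dose comparisons. That needs no new analysis. If unblinded review has already taken place, stating plainly that the objective was addressed descriptively may be the better choice.

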## 2.1.3 Safety Objectives

The safety objectives of the study are to assess the safety and tolerability of the 4 doses of MM- $120 (25, 50, 100 \text{ or } 200 \text{ }\mu\text{g}$  freebase-equivalent) after oral administration in subjects with anxiety symptoms.

## 2.1.4 Exploratory Objectives

Exploratory objectives of the study include:

- To explore dose response on drug effects, altered perception and mystical experience,
- To explore the effect of MM-120 on direct and indirect health-care resource utilization (HCRU) and associated costs (for later analysis, not part of this SAP),
- To explore whether genetic polymorphisms are related to pharmacodynamics,
- To assess blind integrity and to examine whether guess rates are associated with outcomes such as AEs or mood/anxiety symptoms.

#### 2.2 Endpoints

#### 2.2.1 Primary Endpoint

The primary endpoint of the study will be the change in HAM-A Total Score from Baseline to Week 4.

#### 2.2.2 Secondary Endpoints

The key secondary endpoint is change in HAM-A Total Score from Baseline to Week 8.

Other secondary endpoints are:

- Change in HAM-A Total Score from Baseline to End of Study
- Change from Baseline to Day 2 (where applicable), Week 1, Week 2, Week 4, Week 8, and End of Study in the following measures:
  - For depressive symptoms
    - Montgomery-Asberg Depression Rating Scale (MADRS)
  - For anxiety symptoms
    - Clinical Global Impression Severity (CGI-S)
    - Clinical Global Impression Improvement (CGI-I)
    - Patient Global Impression Severity (PGI-S)
    - Patient Global Impression Change (PGI-C)
  - For functional disability
    - Sheehan Disability Scale (SDS)
  - For quality of life
    - EuroQol-5 Dimensions-5 Levels (EQ-5D-5L)
  - For sleep
    - Pittsburgh Sleep Quality Index (PSQI)
  - For sexual function
    - Arizona Sexual Experiences Questionnaire (ASEX)

## 2.2.3 Exploratory Endpoints

Exploratory endpoints for the study are:

- HAM-A response and remission at Weeks 1, 2, 4, 8 and End of Study
- Drug Effect Visual Analog Scale (VAS) assessed on Day 2
- Mystical Experience Questionnaire (MEQ30) assessed on Day 2
- 5-Dimensional Altered States of Consciousness Rating Scale (5D-ASC) assessed on Day 2
- The Treatment Assignment/Blinding Question assessed on Day 2

## **3** INVESTIGATIONAL PLAN

#### 3.1 Study Design

This Phase 2 study will enroll approximately 180 male and female subjects 18-<75 years of age who meet DSM-5 criteria for generalized anxiety disorder (GAD) and have a minimum HAM-A Total Score of 20. Potential subjects who have contraindicated medical or psychiatric conditions or who are taking concomitant medications, supplements or other therapeutics that are contraindicated that cannot be paused will be excluded from the study. Subjects on contraindicated concomitant medications, supplements or other therapeutics at screening will undergo a medication taper prior to advancing to Baseline. Potential study subjects who provide informed consent will have eligibility evaluated/confirmed at 3 visits: Screening, Baseline and Day 1/Randomization. Eligible subjects will be randomized in a 1:1:1:1:1 ratio to receive a single dose of either investigational drug at 4 dose levels (25, 50, 100 or 200 µg MM-120 freebase-equivalent) or placebo in a controlled clinical setting. After Day 1 subjects will have visits on Day 2, Week 1, Week 2, Week 4, Week 8 and Week 12.

## 3.2 Treatment

The study includes 4 dose levels of investigational product (IP): 25, 50, 100, or 200 µg MM-120 freebase-equivalent as well as a placebo arm. Subjects will receive one dose of study drug.

## 3.2.1 Randomization Scheme and Treatment Arm Assignment

Subjects will be randomized in a 1:1:1:1:1 ratio to one of the 4 dose levels of IP or placebo. Randomization will be centrally performed by a Randomization Trial Management System (RTMS). The 5 treatment groups are:

- 1. 25 µg (freebase-equivalent) of MM-120
- 2. 50 µg (freebase-equivalent) of MM-120
- 3. 100 µg (freebase-equivalent) of MM-120
- 4. 200 µg (freebase-equivalent) of MM-120
- 5. Placebo

## 3.2.2 Blinding

This double-blind trial will use a masking technique to blind subjects and study site personnel to

the treatment assignment. The subject, Investigator and Sponsor personnel who are involved in the treatment or clinical evaluation of the subjects will be unaware of the treatment group assignments.

An unblinded statistician, who is not involved with the conduct of the trial, will perform randomization schema reviews and will be unblinded for the duration of the study.

At the end of the trial, and after medical/scientific review has been performed and data have been declared final and complete, the official final database will be locked and unblinded.

## 3.2.3 Dosing Schedule

Subjects will be administered a single dose of capsules to be taken orally on Day 1. Each capsule contains 25  $\mu$ g MM-120 freebase-equivalent, or placebo. Each subject will receive a total of 8 capsules comprising of a combination of active and/or placebo as follows:

- The 25-µg arm consists of 1 active capsule + 7 placebo capsules
- The 50-µg arm consists of 2 active capsule + 6 placebo capsules
- The 100-µg arm consists of 4 active capsule + 4 placebo capsules
- The 200-µg arm consists of 8 active capsules
- The placebo arm consists of 8 placebo capsules

## 3.2.4 Subject Compliance

All subject dosing will occur at the site and be witnessed by the Investigator and/or Dosing Session Monitor(s) and the subject will be monitored at all times until release from the clinic.

## 4 GENERAL CONSIDERATIONS FOR DATA ANALYSIS

Unless otherwise specified, continuous variables will be summarized by presenting the number of non-missing observations, mean, standard deviation, median, 25th and 75th percentiles, minimum, and maximum. Categorical variables will be summarized by presenting the number of subjects and percentage for each category.

Summary results will be provided by treatment group and where appropriate overall for all subjects. All tabulations will be based on pooled data across centers.

Subject data will be listed, sorted by treatment group, investigative center and subject number. When applicable, listings will be sorted by visit and assessment date/time as well.

Analyses will be performed using SAS for Windows statistical software, version 9.4 or higher (SAS, Cary, NC), except where other software may be deemed more appropriate.

CTI Clinical Trial and Consulting Services (Covington, KY) will perform all efficacy and safety statistical analyses.

## 4.1 Analysis Quality Control Procedures

Once all the source verification is complete, all queries are resolved, and the database has been updated appropriately, the database will be locked and made available to CTI Biostatistics for final

analysis.

All SAS programs used to create analysis data sets, tables, and listings will be double programmed. The SAS outputs will be compared and the programs will be updated until the outputs match.

## 4.2 Analysis Sets

The following populations will be defined for the purpose of analysis:

- Randomized Set (RAN) all subjects who received a randomization number, regardless of receiving study drug. Subjects will be analyzed according to the treatment assigned.
- Safety Set (SAF) all subjects who received the double-blind study drug. Subjects will be analyzed according to the actual treatment received.
- Full Analysis Set (FAS) all randomized subjects with a valid baseline HAM-A assessment and at least one valid post-baseline HAM-A assessment. Subjects will be analyzed according to the treatment assigned.
- Per Protocol Set (PPS) All subjects in the full analysis set who had no major protocol deviations deemed as impacting the primary endpoint. Subjects will be analyzed according to the actual treatment received.

An impact assessment will be performed prior to the unblinding of the study. The impact assessment will determine whether a major protocol deviation impacts the primary endpoint thereby leading to the removal of the respective subject(s) from the PPS.

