10.1. Analysis Sets

The following analysis sets will be defined for the statistical analysis. Subjects without valid written study informed consent will be excluded from all analysis sets.

Table 8: MMED008 Analysis Sets

Analysis Set	Description
Randomized Set (RAN)	All subjects who received a randomization number, regardless of receiving trial medication. Subjects will be analyzed according to the treatment assigned.
Safety Set (SAF)	All subjects who received the double-blind study drug. Subjects will be analyzed according to actual treatment received.
Full Analysis Set (FAS)	All subjects in RAN with a valid Baseline HAM-A assessment and at least one valid post-baseline HAM-A assessment. Subjects will be analyzed according to the treatment assigned.
Per Protocol Set (PPS)	All subjects in FAS who had no major protocol deviations deemed as impacting the primary endpoint ^a . Subjects will be analyzed according to the actual treatment received.

^a An impact assessment will be performed prior to the unblinding of the study. The impact assessment will determine whether a major protocol deviation impacts the primary endpoint thereby leading to the removal of the respective subject(s) from the PPS.

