10.2.2. Efficacy Analyses

10.2.2.1. Primary Estimand

The primary estimand quantifies the treatment effect of MM-120 at 4 weeks post-dose administration while accounting for intercurrent events (IEs) with potential confounding effects and IEs leading to study discontinuation prior to the 4-week assessment.

The following attributes describe the primary estimand:

- Population: As defined by the Inclusion/Exclusion criteria
- Endpoint: Change from Baseline to Week 4 in HAM-A Total Score
- Treatment of interest /the randomized treatment: 4 doses of MM-120 (25, 50, 100, or 200 µg free-base equivalent) or placebo as a single-dose treatment.
- Handling of IEs prior to HAM-A assessment at Week 4:
 - Intake or change in concomitant medications/therapies which have potential confounding effects per the impact assessment.
 - Intake of prohibited medications/therapies assessed as "Yes" per the impact assessment.
 - *Policy strategy:* Available data recorded after the IE will be set to missing; such missing data will be imputed/substituted under a Missing Not at Random (MNAR) assumption by borrowing information from the placebo arm subjects (reference-based imputation).
 - IEs leading to study discontinuation due to other reasons.
 - IEs related to the COVID-19 pandemic
 Policy strategy: Available data will be used; missing data will be imputed under a Missing at Random (MAR) assumption, borrowing information from subjects in the same treatment arm.
- Summary measure: Identification of the dose-response curve and estimation of the target dose

Statistical Methods & Analysis

The MCP-Mod methodology (Bretz 2005; Pinheiro 2014) will be employed to assess the primary objective: to investigate the dose-response relationship for different doses of MM-120 versus placebo in change from Baseline in HAM-A Total Score at Week 4. An overview of the steps for the MCP-Mod methodology is given below.

Step 1

The analysis to derive the test statistics is based on an analysis of covariance (ANCOVA) model with the change from Baseline to Week 4 for HAM-A Total Score as a response variable, treatment (placebo and all MM-120 doses), and Baseline value of HAM-A Total Score. Centers will be pooled according to country and region as appropriate and as defined in the SAP prior to unblinding.

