10.2.2.2. Sample Size Determination

A total sample of 180 subjects (36 per dose arm and 36 for the placebo arm) is required to ensure a mean power >87% for an MCP-Mod Analysis rejecting the hypothesis of a constant dose-response curve using the multiple comparisons procedure (MCP), assuming a null placebo response, a maximum standardized effect of 0.6 within the doses range, and a common

standard deviation within the dose arms, if a study-wise one-sided type-1 error rate < 0.05 is required.

The analysis assumes 4 doses of active medication (25, 50, 100, and 200 µg freebase-equivalent) and placebo. The required sample size for each dose arm is 36 subjects.

The R package Dose Finding (https://CRAN.R-project.org/package=DoseFinding) has been used to estimate the sample size and the corresponding power. The power for each model is estimated as shown in Table 9.

Table 9: Study MMED008 Power by Model

Model	Power (%)	
Sigmoid Emax (ED50, hill)		
10, 1	84.5	
100, 5	90.7	
100, 10	91.0	
150, 10	89.9	
Emax (D50 = 100)	83.2	
Linear	85.0	

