## 9 SAMPLE SIZE AND POWER CALCULATIONS

A total sample of 180 subjects, 36 per arm, is required to ensure a mean power >87% for an MCP-Mod Analysis rejecting the hypothesis of a constant dose-response curve using the multiple comparisons procedure (MCP), assuming a null placebo response, a maximum standardized effect of 0.6 within the doses range, and a common standard deviation within the dose arms, if a studywise one-sided type-1 error rate <0.05 is required.

The analysis assumes 4 doses of active medication (25, 50, 100 and 200  $\mu$ g freebase-equivalent) and placebo. The required sample size for each arm is 36 subjects.

The R package Dose Finding (https://CRAN.R-project.org/package=DoseFinding) has been used to estimate the sample size and corresponding power. The power for each model is estimated as shown Table 6.

Table 6	Power by Mode

Model	Power (%)
Sigmoid Emax (ED50, hill)	
10, 1	84.5
100, 5	90.7
100, 10	91.0
150, 10	89.9
Emax (D50 = 100)	83.2
Linear	85.0

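### The full analysis set drops dosed subjects who have no post-baseline HAM-A, although the primary estimand makes no such exclusion and provides for imputing them

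*SAP*

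**What the plan says.** **Analysis set.** SAP 4.2 defines the FAS as "all randomized subjects with a valid baseline HAM-A assessment and at least one valid post-baseline HAM-A assessment". Protocol 10.1 (Table 8) agrees: "All subjects in RAN with a valid Baseline HAM-A assessment and at least one valid post-baseline HAM-A assessment". SAP 6 and Protocol 10.2.2.1 run the primary analysis on this set.

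**Estimand.** Protocol 10.2.2.1 takes its population from the eligibility criteria and says that the estimand accounts for "IEs leading to study discontinuation prior to the 4-week assessment". Under that section and SAP 6.1.1:
- scores after a confounding or prohibited medication judged to have impact are set to missing and imputed from the placebo arm;
- missing scores after other discontinuations are imputed within the subject's own arm under MAR, as are missing scores not due to an intercurrent event.

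Neither document exempts subjects with a baseline score only.

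**Timing.** The Schedule of Activities has no HAM-A on Day 2; the first after dosing is at Week 1, Day 8 ± 1. Protocol 7.2 asks early leavers to return for a visit with the Week 12 assessments, which include HAM-A. SAP 4.3 accepts unscheduled data and counts a HAM-A from Day 2 to Day 11 as Week 1.

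**Other analyses.** The only sensitivity set for the primary endpoint is the Per Protocol Set, a subset of the FAS (SAP 4.2, 6.1). The secondary HAM-A ANCOVAs use the same two sets without imputation (SAP 4.5, 6.3.1). No efficacy analysis uses all randomised subjects.

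**The concern.** The set and the estimand do not match. A subject who is dosed, leaves before Week 1 and gives no later HAM-A belongs to the estimand population and has a missing Week 4 score after a discontinuation. The imputation rules cover exactly that case, yet the FAS clause removes the subject before they can be applied.

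Membership is also decided after dosing, by something that could differ by arm. The protocol itself foresees possible functional unblinding (2.4, 8.4.5) and asks subjects on Day 2 to guess their treatment (8.5.4). If early loss depends on arm, the groups compared are no longer the groups randomised.

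The sharpest case is the subject due placebo-based imputation. That rule withholds credit for the drug after a confounding medication. If the subject is deleted, the arm keeps credit that the estimand would have removed.

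**Working it through.** **1. Two subjects under the plan's own rules.** Both are in an active arm and both start a confounding anxiolytic on Day 3, recorded and judged to have impact.

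| | Subject A | Subject B |
|---|---|---|
| Course | attends Week 1 | leaves on Day 5, gives no HAM-A |
| Scores usable at Week 4 | baseline only (Week 1 set to missing) | baseline only |
| In the FAS | yes | no |
| Handling | imputed from placebo | deleted |

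The usable data are the same. Inclusion turns on a score that the plan then discards. Subject A also shows that the rules already have to impute from baseline alone. This reading takes a valid assessment to mean one that was properly done; I found no definition of the word. If a score set to missing were not valid, both subjects would be excluded, and the conflict with the estimand would be wider.

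**2. The plan's power figure.** Inputs from Protocol 10.2.2.2 and SAP 9: 36 per arm, "study-wise one-sided type-1 error rate < 0.05", "a maximum standardized effect of 0.6 within the doses range", placebo response zero, common SD (set to 1), six candidate shapes at 0, 25, 50, 100 and 200 µg. Stated mean power is (84.5 + 90.7 + 91.0 + 89.9 + 83.2 + 85.0)/6 = 87.4%. Simulating the maximum contrast statistic (175 df, critical value about 2.04) gives 84.6, 90.7, 91.0, 89.9, 83.2 and 85.1, mean 87.4%. The figure reproduces. It assumes 36 analysed subjects in every arm, and no loss allowance is stated.

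**3. Illustration of size.** Neither document gives an early-loss rate, so k = 1 to 3 per active arm, none on placebo, is my assumption. Suppose all k were due placebo-based imputation.
- FAS as written: 36 − k per active arm, 36 on placebo, expected maximum effect 0.6 SD.
- Kept at placebo level: 36 per arm, expected maximum effect 0.6 × (1 − k/36).
- Overstatement: 0.6 × k/36.

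| k | Effect, kept (SD) | Overstatement (SD) | Mean power, as written | Mean power, kept |
|---|---|---|---|---|
| 1 | 0.583 | 0.017 | 86.9% | 85.7% |
| 2 | 0.567 | 0.033 | 86.2% | 83.8% |
| 3 | 0.550 | 0.050 | 85.4% | 81.8% |

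Repeat simulations moved the power figures by up to about 0.2 points. The kept column treats imputed scores as if observed, so it is approximate.

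**4. Other early leavers.** The FAS arm mean differs from the all-randomised arm mean by (k/36) × g, where g is the outcome gap between those who stay and those who leave. With k = 2 and g = 1 SD (assumed) this is 2/36 × 1 = 0.056 SD. The sign of g is unknown. Imputing these subjects under MAR from their own arm moves the estimate little, because a baseline score adds almost no information on outcome (reasoned, not simulated).

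**The case against.** The best defence is that the gap is narrow. The Early Withdrawal visit includes HAM-A, unscheduled scores count, and any HAM-A after dosing day puts the subject in the FAS. A subject who restarts an anxiolytic need not leave: Protocol 7.2 makes discontinuation a matter for discussion. If a HAM-A is then obtained, the subject is in the FAS and the placebo-based rule applies. The rule is lost only when the medication is recorded, judged to have impact, and no post-baseline HAM-A is ever taken. A subject who simply disappears has no later medication on record and falls under MAR, where inclusion hardly matters.

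This limits the number affected, and I accept it. It does not remove the mismatch: the withdrawal visit cannot cover refusal or loss to follow-up, and nothing planned picks up those who remain missing.

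A reader might infer more than the documents support:
- *That these losses are mostly treatment-related and favour the drug.* No loss rates or reasons by arm are given. Placebo subjects who feel nothing and high-dose subjects with a difficult session could both leave, with opposite effects.
- *That every early leaver is excluded.* The withdrawal and unscheduled assessments say otherwise.
- *That the clause accounts for a fall in power from 87.4% to 81.8%.* The first figure assumes nobody is lost. With three dropped per active arm, the comparison is 85.4% against 81.8%.

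**Conclusion.** The FAS clause conflicts with the primary estimand in both documents, and it treats subjects with identical usable data differently. The point stands as a correctable inconsistency, not as evidence of a biased result. Under the assumptions in step 3, for 1 to 3 subjects per active arm, the maximum effect is overstated by 0.017 to 0.050 SD (3 to 8% of 0.6) and mean power differs by about 1 to 4 points. Three per active arm means twelve subjects meeting a narrow condition, so that end of the range is a stress case. For leavers handled under within-arm MAR, the set alone makes little difference; what is missing for them is a sensitivity analysis that departs from MAR.

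**What to change.** In SAP 4.2 and Protocol Table 8, delete the post-baseline clause, so that the FAS is all randomised subjects with a valid Baseline HAM-A. Impute their Week 4 and Week 8 scores under the existing SAP 6.1.1 rules. Add a sensitivity analysis for baseline-only subjects, reference-based or tipping-point, since the MAR rule cannot test its own assumption. Report the number of such subjects and their reasons by arm; SAP 5.1 counts each analysis set and tabulates reasons for early termination, but does not link the two.

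No new data are needed. The cost is a few more imputed values, one more sensitivity analysis and a slightly more conservative estimate. The change to the primary set has to be made before unblinding. The SAP addendum records that the primary endpoint has since been reviewed unblinded; from that stage, keep the FAS as it is and run the wider set as a labelled sensitivity analysis.
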